#### **12.1.4 Lead-in Adverse Events**

Lead-in adverse events will be summarized by preferred term.

#### **12.1.5 Summary of Treatment-emergent Adverse Events**

The following summaries will be provided for the APTS:

- TEAE by SOC and preferred term
- TEAE by preferred term
- TEAE with an incidence > 2% and 5% by preferred term
- Causally related TEAE by SOC and preferred term
- TEAE by intensity (*mild/moderate/severe*), and preferred term
- Causally related TEAE by intensity and preferred term

#### **12.1.6 Deaths**

All the adverse events in patients who died will be listed.

#### **12.1.7 Serious Adverse Events**

All the SAEs will be listed.

Treatment-emergent SAEs for the APTS will be summarized by:

- SOC and preferred term
- Preferred term

#### **12.1.8 Adverse Events Leading to Withdrawal**

All the adverse events leading to withdrawal will be listed.

TEAE leading to withdrawal will be summarized by:

- SOC and preferred term
- preferred term

#### **12.1.9 Adverse Events Related to Tolerability**

Incidence and prevalence rates in every four-week interval will be presented for nausea based on the APTS for events with complete start and stop dates.

Incidence will be defined as the number of patients with a new event in the specified time interval. The denominator in each interval will be the number of patients without the event at

the start of the interval plus the number of patients with an ongoing event at the start of the interval for which the event stops before the end of the interval.

Prevalence will be defined as the number of patients with the event at the start of the interval or who have the event during the interval. The denominator will be the number of patients at the start of the interval.

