8.5 Safety Follow-up Visit/Contact (Visit 14)

The safety follow-up is conducted to capture serious adverse events (SAEs) that occur during the Safety Follow-up Period as well as to follow up on the outcome of adverse events ongoing at the end of the Treatment Period. The safety follow-up may either be conducted as a visit to the site or as a telephone contact. The safety follow-up must be conducted approximately 30 days after the last dose of IMP.

If any new SAEs have occurred since the last assessment at which the patient received IMP, the safety follow-up must, when possible, be a visit to the site.

For adverse events that were ongoing at the end of the Treatment Period and that resolved during the Safety Follow-up Period, the stop date must be recorded. For non-serious adverse events still ongoing at the safety follow-up, the stop date must be recorded as “ongoing”. SAEs must be followed until resolution or the outcome is known.

Patients with a clinical safety laboratory test value that was out-of-range at the Completion or Withdrawal Visit and judged clinically significant must be followed according to accepted medical standards for up to 30 days or until the value normalises or stabilises or a diagnosis or a reasonable explanation has been established. For these patients, safety follow-up visits must be scheduled to allow for a medical examination and/or blood sampling. The investigator must decide whether further safety follow-up visits are required after 30 days. If further safety follow-up visits are made, these must be documented in the patient’s medical record and not in the eCRF.

Patients who withdrew due to elevated AST or ALT values (see section [5.3](#)) should be followed until the values normalise or stabilise or a diagnosis or a reasonable explanation has been established (see section [10.5](#)).

The safety follow-up for patients who withdraw assent/consent must be performed, if at all possible; any information collected will be recorded in the patients’ medical records.

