10.5 Treatment and Follow-up of Adverse Events

Patients with adverse events must be treated in accordance with usual clinical practice at the discretion of the investigator.

Non-serious adverse events must be followed up until resolution or the safety follow-up assessment, whichever comes first. At the safety follow-up, information on new SAEs, if any, and stop dates for previously reported adverse events must be recorded.

It is the responsibility of the investigator to follow up on all SAEs until the patient has recovered, stabilised, or recovered with sequelae, and to report to Lundbeck all relevant new information using the same procedures and timelines as those for the initial report. Relevant information includes discharge summaries, autopsy reports, and medical consultations.

SAEs that are spontaneously reported by a patient to the investigator after the safety follow-up assessment must be handled in the same manner as SAEs that occur during the study. These SAEs will be captured in the GPV database.

Patients with clinically significant out-of-range clinical safety laboratory test values at the Completion or Withdrawal Visit must be followed in accordance with usual clinical practice and be scheduled for a Safety Follow-up Visit to allow for a medical examination and/or blood sampling (see section [8.5](#)).

Patients who withdraw due to elevated AST or ALT values (see section [5.3](#)) must be followed until the values normalise or stabilise or a diagnosis or a reasonable explanation has been established. Additional medical examinations (for example, ultrasound scanning and/or sampling for serology, conjugated bilirubin, INR) should be considered. A gastroenterology or hepatology consultation should also be considered.

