#### **12.1.10 Adverse Events of Special Interest**

Treatment-emergent nausea (preferred term), vomiting (preferred term), insomnia (defined below), and sexual dysfunction (defined below) will be summarised. TEAE related to the musculoskeletal SOC will be summarized.

Insomnia related adverse events and sexual dysfunction related adverse events are defined in [Panel 4](#) and [Panel 5](#).

---

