### **18.5.3 Medication Start and Stop Dates**

In order to assign all medications to an analysis start-and stop phase, missing or incomplete start-or stop dates will be imputed. Ongoing medications at the end of a study will not be assigned a stop phase in that study.

No duration will be calculated for medications with imputed start-or stop date, or for ongoing medications.

For further details, see [Data Handling Plan](#).

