### **18.5.4 Adverse Event Start and Stop Dates**

Incomplete adverse start dates will be imputed before handling of incomplete dates for change in intensity or seriousness.

For further details, see [Data Handling Plan](#).

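### Read as written, SAP 12.1.9 leaves nausea recorded as ongoing, or with a partial or missing stop date, out of the four-weekly nausea rates while the patients stay in the denominators

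*SAP*

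**What the plan says.** SAP 12.1.9 plans nausea incidence and prevalence for each four-week interval. These "will be presented for nausea based on the APTS for events with complete start and stop dates".

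- **Prevalence** counts patients who have nausea at the start of the interval or during it. "The denominator will be the number of patients at the start of the interval".
- **Incidence** counts patients with a new event. Its denominator is the patients free of nausea at the start of the interval, plus those whose current episode ends within it.

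The protocol fixes what the stop-date field can contain. Section 10.5: "Non-serious adverse events must be followed up until resolution or the safety follow-up assessment, whichever comes first". Section 8.5, on the contact about 30 days after the last dose: "For non-serious adverse events still ongoing at the safety follow-up, the stop date must be recorded as" ongoing. Nausea that resolves before that contact gets a stop date, and serious events are followed to a known outcome.

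On dates in general, SAP 18.5.3 gives medications two separate rules: "missing or incomplete start-or stop dates will be imputed", and "Ongoing medications at the end of a study will not be assigned a stop phase in that study". The adverse event counterpart, 18.5.4, states a rule for start dates only: "Incomplete adverse start dates will be imputed before handling of incomplete dates for change in intensity or seriousness". It leaves further detail to the Data Handling Plan. Section 12.1.9 does not cite that plan.

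Elsewhere nausea is summarised without a stop-date condition. SAP 12.1.10: "Treatment-emergent nausea (preferred term), vomiting (preferred term), insomnia (defined below), and sexual dysfunction (defined below) will be summarised". The TEAE tables in 12.1.5 and the listings in 12.1.1 and 12.1.3 have no such condition either.

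**The concern.** An interval prevalence table exists to show whether an adverse event fades or persists. A rule that admits only events with a known end removes the events with the longest course, and removes them from every interval in which they were present. The denominators count patients and do not depend on event dates, so the rates fall instead of being computed on a smaller group.

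Nausea is the drug's most common adverse event in adults (Protocol 1.1.3.3), and long-term tolerability is part of the primary objective. This is the only planned four-weekly nausea display. The other summaries show how many patients had nausea, but not how many still had it at a given time.

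**Working it through.** The plan states no figure to reproduce, so the definitions are applied by counting, and the size is then explored under stated assumptions.

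**1. One patient.** Twenty-six weeks give six four-week intervals and one of two weeks. Take a patient who stays to Week 26, has one non-serious nausea event starting on day 10, and is still nauseated at safety follow-up.

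| | All events counted | 12.1.9 as written |
|---|---|---|
| Prevalence numerator | 1 in all 7 intervals | 0 in all 7 |
| Prevalence denominator | 1 in all 7 | 1 in all 7 |
| Incidence numerator | 1 in interval 1 | 0 |
| Incidence denominator | interval 1 only (the event never stops) | all 7, as free of nausea |

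Both rates can only fall. Prevalence loses the patient from onset onward; incidence loses the patient mainly in the interval of onset.

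**2. Which events are affected.** To be recorded as ongoing, nausea must outlast the last dose by about 30 days. With the adult half-life of 66 hours (Protocol 1.1.3.1), that is 720 h / 66 h = 10.9 half-lives. Protocol 1.1.3.3 also reports that abrupt discontinuation was well tolerated in adults. Few such events may occur.

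**3. Size under assumptions.** From the documents: 850 planned patients and the adult nausea incidence of 20 to 30%. Assumed: one event per affected patient, exponential onset (mean 30 days, within the 182 treatment days), exponential duration (mean 10 days) for resolving events, no withdrawal, and follow-up on day 212. At 20% incidence there are 0.20 × 850 = 170 events.

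- Share with onset in weeks 1-4: (1 − e^(−28/30)) / (1 − e^(−182/30)) = 0.607 / 0.998 = 0.608. True weeks 1-4 incidence is 20% × 0.608 = 12.2%.
- Share of resolving events present in weeks 21-24 (days 140 to 168): [(e^(−140/30) − e^(−168/30)) + 0.5 × e^(−14) × (e^(140/15) − 1)] / 0.998 = 0.0057 + 0.0047 = 0.0104, so prevalence from them is 20% × 0.0104 = 0.21%.
- Unresolved at day 212 under this model alone: 0.5 × e^(−21.2) × (e^(182/15) − 1) / 0.998 = 0.00006, or 0.006%; 170 × 0.00006 = 0.01 events.

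Any material loss therefore needs an added group with persistent nausea. Late prevalence loss is about events dropped / 850. Weeks 1-4 incidence loss is that figure × 0.608, except in the first row, where the few unresolved events start late.

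| Assumption (20% incidence) | Events dropped of 170 | Late prevalence loss | Weeks 1-4 incidence loss |
|---|---|---|---|
| Model above, nothing added | 0.01 | about 0 | about 0 |
| 10% last to the last dose, then resolve in a mean of 10 days | 17 × e^(−3) = 0.85 | 0.10 pp | 0.06 pp |
| Same, mean of 30 days | 17 × e^(−1) = 6.25 | 0.74 pp | 0.45 pp |
| 2% unresolved at follow-up | 3.4 | 0.40 pp | 0.24 pp |
| 10% unresolved at follow-up | 17 | 2.0 pp | 1.22 pp |

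(pp = percentage points.) With 2% unresolved, weeks 21-24 prevalence is 0.40 + 0.98 × 0.21 = 0.60% and is shown as about 0.20%. With 10% it is 2.0 + 0.90 × 0.21 = 2.2% and is shown as about 0.19%. At 30% incidence the losses are 1.5 times as large: 0.6 to 3.0 pp of late prevalence for 2% to 10% unresolved.

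**4. Partial or missing stop dates.** If 5% of resolving events lack a complete stop date (assumed), 0.05 × 170 = 8.5 events drop. Weeks 1-4 incidence of 12.16% is shown as 0.95 × 12.16 = 11.55%. Weeks 21-24 prevalence moves only from 0.21% to 0.95 × 0.21 = 0.20%. This loss falls mainly on early intervals.

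**The case against.** The strongest reply is that the matter may already be settled. SAP 18.5.4 covers adverse event start and stop dates by its heading and refers to the Data Handling Plan, so a stop-date rule may exist there. The SAP's own usage also favours a milder reading: 18.5.3 treats missing or incomplete dates and ongoing medications as separate cases, so complete in 12.1.9 may be meant to exclude partial dates only. Both points lower certainty and stand to that extent. Neither is confirmed in the SAP text, and under the milder reading events with a partial stop date are still lost.

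The second reply concerns size, and it stands. Every unresolved share above is assumed. The 20 to 30% incidence is an adult figure, whereas these patients have completed a lead-in study, and exclusion criterion 3 removes those with certain ongoing related adverse events. Patients who withdraw with persistent nausea also leave later denominators, so the late losses above, computed without withdrawal, may be too high.

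Third, the restriction is disclosed and prespecified, in a descriptive table. That limits the severity, but it does not make the rule suited to showing persistence.

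A reader might infer that the trial will hide substantial persistent nausea, or that its safety conclusion is biased. The documents do not support this: they give no unresolved share, the overall nausea counts are unaffected, and Protocol 17.10.1 rests the primary objective on a clinical evaluation of all safety results. Nor can PAERS be relied on to fill the gap. The documents do not list its items, and Protocol 9.4.10 warns that its counts may differ from those of spontaneous reporting.

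**Conclusion.** The point holds on the plain reading of 12.1.9 and is minor. The rule drops unresolved nausea, and nausea with a partial or missing stop date, while keeping the patients in the denominators. The direction is downward, and the loss is selective for persistent nausea. The size is unknown and may be near zero; the 0.4 to 2.0 point range for late prevalence depends on the assumed 2% to 10% unresolved share at 20% incidence. Only this descriptive table is affected. The conclusion would lapse for ongoing events if the Data Handling Plan counts them as present, but the SAP wording would then still need to be brought into line.

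**What to change.** In SAP 12.1.9, replace the restriction to fully dated events with a rule on these lines:

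- **Start dates:** use them as imputed under 18.5.4.
- **Recorded as ongoing:** include the event and count it as present through the patient's last day in the table's time frame. That day is the earlier of the Completion/Withdrawal Visit (or the last attended visit if that one is missing) and the end of the last interval.
- **Partial stop date:** include the event, with the stop imputed to the end of the known month or year but no later than that same day.
- **Stop date wholly missing and not recorded as ongoing:** count the event in its interval of onset, but do not carry it to the end in the main display. Report the number of such events and show them carried forward in a sensitivity display.

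Report the counts of ongoing, partial-stop and missing-stop events beside the table. If the Data Handling Plan already holds such a rule, cite it in 12.1.9 and delete the conflicting wording.

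Missing stops are kept apart because carrying them forward can err upward by as much as the present rule errs downward: with 5% of events so affected at 20% incidence, it adds about 0.05 × 20% = 1.0 percentage point to late prevalence that is otherwise about 0.2%. Month-end imputation lengthens an event by at most one month, so its effect on late intervals is small.

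The cost is one SAP paragraph, minor programming, and late-interval rates that may look slightly less favourable.

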# 2 Study Design

This is an interventional, multi-national, multi-site, open-label, flexible-dose, long-term extension study in child and adolescent patients with MDD who completed one of the double-blind, placebo-controlled, active-reference studies 12709A and 12710A.

The Baseline Visit, hereafter referred to as OLEXA, of this extension study, will be Visit 12 (Completion Visit) of lead-in Study 12709A or 12710A, see section 18.1.

The dosage of vortioxetine will be initiated at 5 mg/day for the first 2 days prior to receiving 10 mg/day. The target dose is 10 mg/day; however, the investigator has the possibility to adjust the dose in case of unsatisfactory response up to 20 mg or in case of dose-limiting adverse events. The dose can be up or down titrated with 5 mg/day. The patient should receive the same dose for 2 days before being up-titrated to a new dose. Changes in dosing may occur at any site visit during the treatment course at the investigator's discretion but the maximum dose may not exceed 20 mg/day.

[figure not shown]
For subset of patients participating in the palatability assessment (patients enrolled in Bulgaria, Estonia, Germany, Latvia, Mexico, Poland, Russia, Serbia, Ukraine, and Colombia), palatability and acceptability of vortioxetine oral drops will be assessed after intake of a single dose (5-20 mg) corresponding to the patient's current vortioxetine dose (instead of their vortioxetine tablet on that day). The assessment can be done at any visit to the clinic from Week 4 to Week 18 (i.e., at Visits 5, 7, 9, or 11).

The treatment period is 26 weeks. The total study duration per patient from OLEXA to the end of follow-up will be approximately 30 weeks.

If possible, patients who withdraw are to be seen for a withdrawal visit as soon as possible and they will be contacted for a safety follow-up visit 4 weeks after withdrawal.

The study design is presented in [Panel 1](#).

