## **4 Analysis Sets**

The following analysis sets will be used to analyse and present the data:

- all-patients-treated set (APTS) – all patients who took at least one dose of vortioxetine in 12712A.
- full-analysis set (FAS) – all patients in the APTS with valid OLEXA assessment and at least one valid post-OLEXA assessment of the CDRS-R total score.

The safety analyses will be based on the APTS. The efficacy analyses will be based on the FAS.

The patients and data will be classified into the analysis sets according to the definitions above after the study database has been released.

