Recent and concomitant medication	✓ g	✓	✓	✓	✓	✓	✓	✓	✓	✓	✓	✓	✓		
Pregnancy test j	✓ e				✓								✓		
Drug and alcohol screen e,k															

a This visit should take place as soon as possible after the patient withdraws from the study.

b This can be a telephone contact, unless an SAE has occurred since the last visit or unless there was a clinically significant abnormal safety laboratory test value at the last visit. In such cases, safety follow-up(s) must be scheduled to allow for a medical examination and/or blood/urine sampling. Further safety follow-up visits beyond 30 days may be needed as judged by the investigator (if further safety follow-up visits are performed, these must be recorded in the patient's medical record, and not in the eCRF).

c A telephone contact. The patient and/or legal representative and/or the investigator can request an unscheduled site visit to discuss their current dose. During such an unscheduled site visit, the CDRS-R, CGI-S, CGI-I, PAERS and C-SSRS must be performed.

d If the date of a patient visit does not conform to the study plan, subsequent visits should be planned to maintain the visit schedule relative to Baseline Extension A. The number of days between 2 visits must not exceed the number of days for which IMP is provided for in the drug kit.

e Values from assessments and procedures conducted at Visit 12 (Completion Visit) of Study 12709A or 12710A will be the Baseline Extension A Visit values for this study (12712A).

f The assessment of the CGI-I should be in reference to Baseline A in the lead-in studies.

g Ongoing adverse events and concomitant medications (at Completion Visit 12 in Study 12709A or 12710A) will be transcribed to the eCRF Adverse Event Form and Concomitant Medication Form.

h Only for adverse events ongoing at Completion/Withdrawal and new SAEs.

i The 12712A Hormones panel is to be collected using a separate study-specific kit

j Females >10 years of age or female patients at lower age judged by the investigator to be of childbearing potential. Additional pregnancy tests during the study will be performed according to local requirements.

Females <11 years will be tested using a urine hCG test and females >11 years will be tested using a blood hCG test.

- k It is not mandatory to screen for drugs and/or alcohol. However, it can be performed at any visit, at the discretion of the investigator.

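### The last four-week nausea interval in SAP 12.1.9 holds only two treatment weeks, so its incidence is about halved by construction; the denominator also omits a condition that patients are still under observation

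*SAP*

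**What the plan says.** SAP 12.1.9 states: "Incidence and prevalence rates in every four-week interval will be presented for nausea based on the APTS". The APTS is defined in SAP section 4 as "all patients who took at least one dose of vortioxetine in 12712A".

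The incidence numerator is the number of patients with a new event in the interval. For the base, the SAP says "The denominator in each interval will be the number of patients without the event at" and continues "the start of the interval plus the number of patients with an ongoing event at the start of the interval", provided that the event ends before the interval does. For prevalence it says "The denominator will be the number of patients at the start of the interval".

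Two other places fix how much time can be observed. SAP section 2 says "The treatment period is 26 weeks". At the safety follow-up, adverse events are recorded under footnote h of SAP Table 1: "Only for adverse events ongoing at Completion/Withdrawal and new SAEs". Protocol 8.5 describes the same scope for that contact. Protocol 8.4 limits data after withdrawal to the Withdrawal Visit and adverse event follow-up.

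SAP 12.1.9 does not use patient-time, does not say how the last interval is bounded, and does not say what happens to patients who have left the study.

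**The concern.** A proportion of patients with a new event depends on how long each patient is watched. Rows in an interval table can be compared only if the intervals are equally long, or if the measure allows for their length. Four does not divide 26, so the last interval cannot be like the others.

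Among the adverse event summaries in SAP 12.1, this is the only one split by time interval. Nausea is named in Protocol 1.1.3.3 as the most common adverse event in adults and among the most frequent in the paediatric pharmacokinetic study. A reader will naturally use the table to see whether nausea fades with continued treatment. A low last row would look like improving tolerability when it may show only a shorter period of observation.

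The second, smaller issue is that the incidence base has no stated condition on still being under observation. Two programmers could produce different tables from the same paragraph.

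**Working it through.** **Inputs from the documents.** Interval length is 4 weeks (SAP 12.1.9). Treatment is 26 weeks (SAP section 2). The Visit 13 window is ±5 days (SAP Table 1). Planned size is about 850 (SAP section 15). That size reproduces: 1200 × 0.80 × 0.85 = 816 and 1200 × 0.85 × 0.85 = 867, with midpoint 841.5. The SAP states no nausea figure to reproduce.

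**Assumptions, not in the documents.** The true risk of new nausea is constant at 2% per four weeks (1% and 5% also tried). Withdrawal over 26 weeks is 0% to 40%.

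**Step 1: length of the last interval.** 26 / 4 = 6.5. Six full intervals cover 6 × 28 = 168 days and treatment covers 26 × 7 = 182 days. The seventh interval (days 169-196) therefore has 182 − 168 = 14 treatment days.

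**Step 2: effect of the short interval alone.** With a constant hazard and four-week risk r, the risk over d days is 1 − (1 − r)^(d/28). For r = 0.02 and d = 14 this is 1 − 0.98^0.5 = 1.005%, a ratio of 0.50 to the full-interval 2.0%. The ratio is 0.50 at r = 1% and 0.51 at r = 5%. If Visit 13 falls 5 days early or late (d = 9 or 19), the ratio at 2% is 0.32 or 0.68. No withdrawal is needed for any of this.

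**Step 3: the two readings of the denominator.** These figures use a 2% risk and a constant withdrawal hazard. Reading A counts patients still in the study at the start of the interval. Reading B counts every APTS patient without the event, including those who have left.

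| Withdrawal over 26 weeks | A: intervals 1-6 | A: interval 7 | B: interval 1 | B: interval 6 | B: interval 7 |
|---|---|---|---|---|---|
| 0% | 2.00% | 1.01% | 2.00% | 2.00% | 1.01% |
| 10% | 1.98% | 1.00% | 1.98% | 1.83% | 0.91% |
| 20% | 1.97% | 1.00% | 1.97% | 1.66% | 0.81% |
| 40% | 1.92% | 0.99% | 1.92% | 1.30% | 0.62% |

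A simpler pattern spreads withdrawal evenly over 26 weeks and ignores losses within an interval. For reading B at 20% withdrawal, Weeks 21-24 then show 2.0% × (1 − 0.20 × 20/26) = 1.69%, and the last interval shows 1.005% × (1 − 0.20 × 24/26) = 0.82%. At 30% withdrawal the last interval is 1.005% × (1 − 0.30 × 24/26) = 0.73%.

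**Step 4: the remedy.** On patient-time, the constant hazard is −ln(0.98) = 0.0202 per four weeks. Every interval, including the seventh, gives 2.02 per 100 four-week patient-periods at each withdrawal rate tried. Using reading A alone flattens intervals 1-6 but leaves the seventh at about 1.0%.

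**The case against.** The strongest objection concerns the denominator. A reader might infer that the SAP keeps withdrawn patients in the base, so that nausea seems to decline through all the late rows, by up to 64% in the last one (0.73% against 2.0% at 30% withdrawal). The documents do not support that. SAP 12.1.9 is silent on withdrawn patients. Its prevalence base, "The denominator will be the number of patients at the start of the interval", makes most sense as a count that shrinks as patients leave. Naming the APTS identifies the analysis set and need not define the risk set. Incidence and prevalence also normally have different bases, so that difference is not a fault in itself. This objection stands: what is missing is a stated condition, and every figure beyond the halved last row depends on a contested reading and on withdrawal rates that the documents do not give.

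On the last interval, it can be said that no Weeks 25-28 row is written into the plan, that the exposure categories in SAP section 9 do break at 182 days, and that the Data Handling Plan may hold a rule. These points soften the concern without answering it. The section 9 break shows that the end of treatment was considered there, but 12.1.9 has no equivalent. The Data Handling Plan is not among the documents, and 12.1.9 does not refer to it, although other SAP sections do. Relabelling the row as two weeks would warn the reader, but the proportions would still not be comparable.

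On importance, the table is descriptive. PAERS is also collected at each treatment-period visit with graphical presentations planned, and Protocol 17.10.1 rests the primary objective on an overall clinical evaluation. That limits the weight of the point, and the SAP does not itself state that the table is meant to show fading nausea.

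**Conclusion.** The point holds for the last interval. Followed as written, SAP 12.1.9 gives a final row with half the observation time of the others, so a constant 2.0% four-week risk appears as about 1.0% under either reading of the denominator and with no withdrawal at all. The ratio is about 0.50 for true risks of 1% to 5%, and ranges from 0.32 to 0.68 across the Visit 13 window. This rests on a constant hazard and on the seventh interval not being shortened, merged or rescaled by a rule held elsewhere.

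The denominator part holds only as an omission. If programmers count patients still in the study, intervals 1-6 stay flat. Dilution before the last row arises only under the literal reading.

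The consequence is one potentially misleading row in a descriptive tolerability table. Planned size and the other adverse event summaries are unaffected. It is worth correcting because the row bears on the primary objective and the change is cheap.

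**What to change.** In SAP 12.1.9:

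- Limit both denominators to patients still in the study and on IMP at the start of the interval. For incidence, keep the existing rule on ongoing events within that group.
- Define the last interval as Weeks 25-26, from day 169 to the end of treatment, and label it so. Withdrawal Visits at other weeks stay in the interval in which they fall.
- Report incidence per patient-time at risk in each interval, or at least alongside the proportions. Count time to the first new event, last dose, withdrawal or interval end, and leave out time with ongoing nausea.
- If the Data Handling Plan already holds such rules, cite it in this section.

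The cost is a revised paragraph and one reprogrammed table, with no new data. Patient-time rates are less familiar to clinical readers, and the last row will look less favourable than it would under the present rule.
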